MM represents a safe strategy for treating mood and anxiety disorders and potentially aspects of attentional performance in a mTBI population. However due to this population’s post-traumatic cognitive impairments, MM is a less accessible therapeutic strategy than it otherwise would be. MUSE, through its provision of NF and gamification, has the potential to help TBI patients initiate, sustain, and maintain a meditation practice. If MUSE outperforms MM on affective or cognitive outcome measurements, this study could function as a pilot study, informing future investigations of the product. If MUSE ultimately holds up in more rigorous studies, it should be recommended as a therapeutic tool to mTBI patients. If on the other hand, MUSE does not show any benefits over a regular practice of MM, the device would not be considered cost-effective and should therefore not be recommended to mTBI patients.

Specific Aims:

Aim 1: Evaluate within group differences, whether a daily, six-week practice of NF-MM or MM or a no-treatment control leads to pre- versus post-treatment changes in affective, cognitive, or mindfulness-associated variables.

Aim 2: Evaluate across-group differences, whether NF-MM outperforms MM in affective, cognitive, or mindfulness-associated variables, or whether NF-MM or MM differ from a no-treatment control group.

Aim 3: Evaluate the change in mindful attention (as measured by EEG) between NF-MM and MM groups and the no-treatment control group at the end of the intervention.

Aim 4: Evaluate the relationship between the degree of mindful attention (as measured by EEG) and affective and cognitive variables across NF-MM/MM groups as well as the no-treatment control group.

Aim 5: Evaluate acceptability of and attitudes toward NF-MM in TBI patients.

Subject Selection

Inclusion criteria: 1) history of mild-moderate TBI (per ACRM guidelines), 2) significant complaint of impaired attention or concentration, 3) ages 18-65, 4) >1 year since TBI, 5) significant cognitive function to participate in neurofeedback and mindfulness meditation, 6) has daily access to a smart phone, 7) no significant medication changes planned for the duration of the study, 8) has not had a significant meditation practice in the past.

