Device to be used: MUSE hardware and Calm app software. MUSE is a consumer product, a “brain-sensing headband” lined with 7 frontotemporal EEG sensors that detect alpha, beta, delta, gamma, and theta waves. MUSE training begins with a calibration task whereby participants’ EEG waves are compared between an attentional and relaxation task. The Calm app guides participants through a mindfulness meditation exercise, providing instructions for users to close their eyes, relax their body, and pay careful attention to their breath. During this meditative practice, EEG signals are fed back to patients through auditory feedback, a calm

versus noisy wind. When participants are consistently in a relaxed state, they will hear birds chirping. Through this auditory feedback, patients are trained to maximize their relaxed, attentive states, and minimize their distracted, tense states. User's performance and progress is tracked over time on a mobile device. MM controls will use a custom version of the Calm software for directed meditation without the MUSE EEG NF component. For further details regarding details of the MUSE device, please see attached documents.

Data to be collected:

- 1) Outcome measurements:
 - a. Cognitive assessments: Trail-Making Test (from D-KEFS), Symbol-Digit Coding, WAIS-IV Digit Span (forward, backward, sequencing), the Connor's Continuous Performance Test 3rd version (CPT-3), and the Self Efficacy (SEsx) scale.
 - b. Affective assessments: 1) Beck Anxiety Inventory (BAI), 2) Beck Depression Inventory (BDI-II), 3) Neurobehavioral Symptom Inventory (NSI)
 - c. Mindfulness assessment: Cognitive and Affective Mindfulness Scale – Revised (CAMS-R)
- 2) Compliance to intervention: The Calm app will track daily meditation practice adherence in both the NF-MM and the MM groups.
- 3) EEG data for NF-MM or MM groups: The Calm app will track the percentage of time participants in the NF-MM group spend in a relaxed attentive state during training. Additionally at the end of the 6-week intervention, both NF-MM and MM groups will be asked to meditate while connected to EEG leads without auditory neurofeedback. The percentage of time spent in a calm, neural, and active state will be assessed here as well.

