- 4) Qualitative assessment: Both NF-MM and MM groups will undergo a very brief qualitative interview at their post-treatment session to inquire on their subjective experience with MM with or without NF. The MM will then receive a MUSE device and practice NF-MM for two additional weeks, after which point they will receive a phone call with further questioning regarding their experience with MM with or without NF.

Biostatistical Analysis

First, we will power this study using the effect size that we calculate from the cognitive MUSE data collected by Bhayee et al. Then, we will compare our NF-MM, MM, and no-treatment control groups. We will contrast the three groups' cognitive outcomes in trail-making, symbol-digit coding, WAIS-IV digit spans. We will then compare affective outcomes using the Beck Anxiety Inventory, Beck Depression Inventory and Neurobehavioral Symptom Inventory. Finally we will compare mindfulness data from the Cognitive and Affective Mindfulness Scale. The continuous variables from the cognitive and affective measures will be analyzed with linear regression. The statistical contribution of demographic variables will be assessed using mixed effects models. We plan to perform post-hoc analysis for multiple comparisons.

Risks and Discomforts

Complications of procedures: We do not anticipate significant adverse effects from the use of MUSE technology, as it is already in wide use in the general population without reports of any significant harm. However, other neurofeedback studies have documented patient complaints of fatigue, feeling "spacey," anxiety, irritability, headache, or difficulty falling asleep (Hammond et al. 2011). Subjects will be able to contact study staff during daytime hours with questions or concerns regarding the possibility of such adverse effects. If these symptoms are believed to be stemming directly from use of MUSE and are intolerable for patients, they will be instructed to discontinue participation in the study.

Device complications/malfunctions: While it is not expected, it is possible for the MUSE device to malfunction. Participants will be able to email or call with tech support questions during standard business hours. Study staff members will call patients back to troubleshoot. While

equipment malfunction could interfere with data collection, it will not put patients at any risk of harm.

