Potential benefits to participants: Based on the mindfulness meditation literature, participation in the NF-MM or MM arms of this study is likely to have a positive impact on a patient's mood, anxiety, and biological stress levels. It may also help with attentional impairment. Individuals in the no-treatment control group will continue with care as usual. They are not expected to benefit directly from participation in this study.

All participants in all groups will receive a Muse device in compensation for completing the study.

Potential benefits to society (e.g., increased understanding of disease processes): Information from this study could potentially be useful to mTBI patients on a population level. If NF-MM is shown to significantly outperform standard MM in terms of psychological and cognitive performance, mTBI patients and their clinicians may want to consider using MUSE following brain injury. If NF does not enhance participants' practice of MM, mTBI patients and their clinicians will want to recommend against the use of the device, as its cost does not bear out in improved outcomes. If the NF-MM or MM groups outperform the no-treatment control group, results will suggest that various types of meditation interventions may be useful for affective or cognitive symptoms in individuals with traumatic brain injury.

Monitoring and QA

Independent monitoring of source data: Study staff, physicians or psychologists, will be responsible for reviewing the accuracy and completeness of form entries, case documents, and informed consent.

Safety and outcomes monitoring: Safety and efficacy data will be reviewed on a weekly basis through email or phone correspondence between participants and either a physician or psychologist study staff member. If the practice of meditation or use of neurofeedback is causing significant psychological distress or physical discomfort, the patient will be advised to discontinue participation.

Adverse event reporting guidelines: All reports of adverse psychological and physical effects will be relayed directly to the study PI and to MUSE.

References:

<http://doi.org/10.1016/j.psychres.2013.09.002>

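### No primary outcome, primary contrast or error control across scores is set, and two sections give different conditions for MUSE outperforming MM

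*Combined protocol and SAP*

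**What the plan says.** Aim 2, under Specific Aims, asks "whether NF-MM outperforms MM in affective, cognitive, or mindfulness-associated variables", and whether either arm differs from no treatment. No variable and no contrast is put first.

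Biostatistical Analysis compares three groups on "cognitive outcomes in trail-making, symbol-digit coding, WAIS-IV digit spans", on three affective scales (BAI, BDI-II, NSI) and on the CAMS-R mindfulness scale. It states no significance level. On multiplicity it says only "We plan to perform post-hoc analysis for multiple comparisons".

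The list under Data to be collected is longer. It also has the CPT-3 and the self-efficacy scale (SEsx), which the analysis section does not name.

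Two sections say what would follow from a MUSE advantage:

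- Rationale behind the proposed research: "If MUSE outperforms MM on affective or cognitive outcome measurements, this study could function as a pilot study, informing future investigations of the product". A recommendation is held back until more rigorous studies. The opposite case is that "MUSE does not show any benefits over a regular practice of MM".
- Potential benefits to society: "If NF-MM is shown to significantly outperform standard MM in terms of psychological and cognitive performance", patients and clinicians may want to consider the device.

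**The concern.** With no primary score, the comparison of NF-MM with MM is spread over many scores. The Rationale wording lets an advantage in either domain count, and treats the device as unsuccessful only if there is no benefit at all. On that wording, the claim can rest on whichever score happens to come out best, chosen after the data are seen.

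The multiplicity sentence does not close this gap. It follows a three-group comparison, so it may mean pairwise tests between groups. Even a sound correction of that kind, applied within each score, leaves the error across scores uncontrolled.

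The two sections can also disagree on the same data. A difference on one affective scale and on no cognitive test would meet the Rationale condition and fail the one under Potential benefits to society. Nothing in the plan says which governs.

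**Working it through.** The plan states no significance level, power or familywise error rate, so there is no figure of its own to reproduce.

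**Inputs**
- Arms: 30 subjects in all, of whom 10 are no-treatment controls (Treatment assignment and randomization). That leaves 20 for NF-MM and MM, taken as about 10 each (assumption).
- Level: two-sided 0.05 per test, so 0.025 in MUSE's favour (assumption).
- Affective scores named for analysis: 3. *Psychological* under Potential benefits to society is read as these three (assumption).
- Cognitive scores named for analysis: trail-making 1, symbol-digit 1, digit span 1 or 3, so 3 or 5.
- Affective plus cognitive: 3 + 3 = 6, or 3 + 5 = 8. Adding one score each for CPT-3 and SEsx to the eight gives 10. CAMS-R is left out because both conditions concern affective (or psychological) and cognitive results, and the plan lists mindfulness separately.

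**Formulas for k independent scores and no true effect**
- At least one false difference: 1 − 0.95^k. For k = 6, 8, 10: 0.265, 0.337, 0.401.
- At least one in MUSE's favour: 1 − 0.975^k. For k = 6, 8, 10: 0.141, 0.183, 0.224.
- At least one in each domain in MUSE's favour, with 3 affective and c cognitive scores: (1 − 0.975^3)(1 − 0.975^c). For c = 3, 5, 7: 0.005, 0.009, 0.012.

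**With correlated scores.** Correlated rows are simulated: 10 per arm, no effect, equal correlation between all scores, two-sample t-tests of NF-MM v MM, 100,000 trials per row.

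| Scores | Correlation | Any false difference | In MUSE's favour | Both domains in MUSE's favour |
|---|---|---|---|---|
| 6 | 0 | 26.5% | 14.1% | 0.5% |
| 6 | 0.3 | 24.4% | 12.4% | 1.4% |
| 6 | 0.5 | 21.1% | 10.6% | 2.1% |
| 8 | 0 | 33.7% | 18.3% | 0.9% |
| 8 | 0.3 | 30.2% | 15.1% | 2.0% |
| 8 | 0.5 | 25.7% | 12.9% | 2.9% |
| 10 | 0 | 40.1% | 22.4% | 1.2% |
| 10 | 0.3 | 35.6% | 18.2% | 2.6% |
| 10 | 0.5 | 29.4% | 14.7% | 3.3% |

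**If the multiplicity sentence means Tukey comparisons of the three groups within each score.** For 6 to 8 scores, the NF-MM v MM error across scores falls to about 9–15% in either direction and 5–8% in MUSE's favour. That is still two to three times 2.5%.

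**With one named primary score.** The error is 5% in either direction and 2.5% in MUSE's favour.

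**The case against.** Four points can be made against the concern.

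1. Neither section states a formal success rule. Both are narrative, and counting a win on any single measure is an interpretation of the Rationale. This stands. It is also part of the defect, since the analysis section supplies no rule in their place.
2. The Rationale calls the study a possible pilot, and a chance win there leads only to another study. This stands. A reader might infer that the inflated error feeds straight into advice to patients. The documents do not support that: the advice is attached to the *and* condition, whose false-win rate is about 0.5–3%, close to nominal.
3. The multiplicity sentence could be a loosely worded correction across scores. It could, but it names no method, family or error rate, so it cannot be relied on as one.
4. Strict adjustment is costly at this size. Under a normal approximation, the standardised difference detectable with 80% power at 10 per arm is (1.960 + 0.842) × √(2/10) = 1.25. At the first Holm step over eight scores, level 0.05/8 = 0.00625, it is (2.734 + 0.842) × √(2/10) = 1.60. This stands, and is a reason to report secondary scores as estimates rather than require Holm throughout.

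Two further stronger readings fail. A reader might infer that a chance MUSE win is likely, but no NF-MM v MM figure above reaches one half. A reader might also multiply scores by three contrasts as if independent: for eight scores, 1 − 0.95^24 = 71%. The contrasts share arms, so this overstates the error; simulation with uncorrelated scores gives about 65%. That figure also covers all contrasts, not the MUSE claim.

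**Conclusion.** The concern holds in a limited form. No primary outcome, primary contrast or error control across scores is stated, and the two sections set different conditions for MUSE outperforming MM.

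Read as either domain sufficing, the Rationale condition gives a false MUSE advantage in about 11–18% of trials on the six to eight scores named for analysis, roughly four to seven times the nominal 2.5%. It reaches 22% if CPT-3 and SEsx are added and scores are independent. It is lower under Tukey within scores, and near nominal under the *and* condition.

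These figures assume two-sided 0.05, about 10 per arm, one score per test apart from digit span, and equal correlations from 0 to 0.5. Further trail-making or CPT-3 subscores would raise them, but the documents do not say that any will be analysed.

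**What to change.** Make a dated amendment before any post-treatment outcome is compared by arm. Timing matters: depressive symptoms were already compared by arm after 10 subjects for allocation, and Monitoring and QA provides for weekly review of efficacy data.

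1. Make NF-MM v MM at post-treatment, adjusted for baseline, the primary contrast.
2. Name one cognitive or attention score as primary. This fits the Background, which places the added benefit of neurofeedback in attention, and the entry criterion of an attention complaint. Take it from the Biostatistical Analysis list, or specify one CPT-3 score and add CPT-3 to that list.
3. Define outperforming identically in the Rationale and in Potential benefits to society, as a win on that score.
4. Replace the multiplicity sentence with: all other scores and contrasts are reported as estimates with 95% confidence intervals, labelled exploratory, with Holm adjustment if any secondary significance claim is made.

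The cost is wording only; no visit, test or subject is added. The downside is that secondary scores can no longer carry the device claim on their own. The change does not add power. At 10 per arm, a standardised difference of 0.8 has about 43% power (normal approximation, no baseline adjustment), so a missed primary should be reported with its interval and not read as absence of benefit.

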Treatment assignment and randomization, if applicable: Patients meeting study criteria will be randomized into one of two groups, either the NF-MM or MM group on a rolling admission. Preliminary assessment after 10 subjects enrolled in the study, demonstrated that participants in the intervention (MUSE) group had higher rates of depressive symptoms than participants in the control group. In order to balance these groups, we subsequently have decided to stratify by depression scores, such that the next five enrolled participants would be placed in the MUSE group if they had lower than average (for the study) BDI scores or the control group if they had higher than average (for the study) BDI scores. After these five subjects were enrolled, we will recalculate average BDI scores and decide whether to continue to stratify by depression scores or not.

Additionally, we have decided to add a no-treatment control group of 10 subjects. These individuals will be recruited after the first 20 subjects complete the trial. Thus, 30 subjects in total will now be part of this study.

Study Procedures

Study Site: Pre- and post-treatment assessments will be performed in outpatient offices at SRH in Charlestown or Cambridge (for those enrolled in the SRH study). MUSE training session will occur during the pre-treatment assessment session for the intervention groups. This training will last approximately 30 minutes and include a MM session with or without auditory NF.

Participants will then perform their 6 weeks of NF-MM with MUSE or MM without MUSE at their homes. Study staff will also call participants on a weekly basis, to remind patients to practice and provide technical support. A post-treatment assessment session will take place within one week of completion of the intervention. Those in the no-treatment control group, will simply undergo pre- and post-neuropsychological testing 6 weeks apart and receive meditation and MUSE training at their final 6-week visit.

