Psychological non medical risk: Meditation practice has very infrequent adverse effects. However in patients with severe mental illness (severe depression, suicidality, disabling anxiety, tendency toward dissociation), spending time silent, alone with one's thought in a repetitive practice can rarely exacerbate psychopathology. These patients will be carefully screened and excluded from participating in the study. If MM is stirring up unpleasant thoughts and feelings, they will be able to reach study staff members during business hours, and if necessary will be discontinued from the study. Participants in this study will also be asked to fill out the BDI-II form during pre- and post-test visits. A contingency plan is in place if participants exhibit suicidal ideation. Please see the attached document.

Disclosure of Confidential Information: All patient information will be kept confidential in this study and will not be shared outside of study collaborators. Subjects' data that is collected via MUSE will also be safeguarded. Please see the attached data handling form from MUSE. Importantly, subjects data that is stored on MUSE does not include personal health information. It includes the participant's username, email, frequency of MM training, and EEG waves during meditation. Users' accounts are also password protected.

Minimization of Risks: Risks of loss of privacy will remain as with any study. For this reason, all data collected from participants will be kept in a secure, password protected database. Trackable correspondence with participants, ie email, will be conducted through a secure exchanger. Participants' data will be de-identified at the onset of the study and assigned a subject number that will be used to keep track of their study data. A key linking patient's names and their study number will only be available to key research personnel. All study data will be stored in a secure location, maintained either electronically on a password protected computer or if on paper, in a locked cabinet in a private office or office requiring a security badge to enter. Printed computer data that is no longer needed for research purposes will be properly disposed of in secure, confidential medical paperwork waste bins.

Potential Benefits

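### People who stop because of symptoms leave the study with no post-treatment affective scores described, which could slightly favour meditation over no treatment

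*Combined protocol and SAP*

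**What the plan says.** Three places in the combined protocol and SAP deal with people who do badly on the intervention.

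- Risks and Discomforts, Complications of procedures: if symptoms are attributed to MUSE "and are intolerable for patients, they will be instructed to discontinue participation in the study".
- Risks and Discomforts, Psychological non medical risk: people for whom meditation stirs up unpleasant thoughts and feelings can contact staff, and "if necessary will be discontinued from the study".
- Monitoring and QA, Safety and outcomes monitoring: if meditation or neurofeedback "is causing significant psychological distress or physical discomfort, the patient will be advised to discontinue participation".

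On outcome timing, Study Site says: "A post-treatment assessment session will take place within one week of completion of the intervention". The BDI-II is placed at the pre- and post-test visits only. Controls are tested twice, 6 weeks apart, and "receive meditation and MUSE training at their final 6-week visit".

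On analysis, Biostatistical Analysis says: "The continuous variables from the cognitive and affective measures will be analyzed with linear regression". Mixed models are mentioned only for demographic variables. No analysis set and no rule for missing post-treatment scores is given. Weekly phone or email contact reviews both safety and efficacy data, but no BAI, BDI-II or NSI is named there. Adverse effects are relayed to the principal investigator and to MUSE, with no count of stops by arm planned. The study schematic, survey tools and suicidal-ideation contingency plan are attachments not available here.

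**The concern.** None of the three rules separates stopping the practice from leaving follow-up. Followed as written, they remove a person from the outcome data for a reason related to the outcome. The triggers include anxiety, irritability and psychological distress, which overlap with what the affective scales measure. The overlap is partial, because headache, fatigue and physical discomfort also count.

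The loss is also one-sided. Controls have nothing to stop until the visit at which they are retested, so these triggers cannot remove a control first, although controls may withdraw for other reasons. Mixed models would not repair the gap: with one score before and one after, no intermediate score informs a stopper's missing value.

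Aim 2 compares each meditation arm with no treatment on affective variables. The section on potential benefits to society would read a better result in the meditation groups as a sign that such interventions may be useful. With about 10 people per arm, each stop is a tenth of that arm's data.

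**Working it through.** The plan gives no significance level, SD, effect size or dropout rate, so it has no figure to reproduce. The check is of direction and size.

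**Inputs.** From Treatment assignment and randomization: 10 controls and 20 people in the two meditation arms. Assumed: 10 per meditation arm; no true effect; two-sided 5% test; 6-week change scores in units of their SD (higher is worse); a pooled t-test standing in for a regression with a group term; the k most distressed people stop; correlation ρ between distress at stopping and 6-week change.

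**Shift per stop.** The expected two largest of 10 standard normal values are 1.539 and 1.001, which sum to 2.540. The mean of those who remain moves by −ρ × 1.539/9 for one stop and −ρ × 2.540/8 for two. The standard error of a 10 v 10 difference is √(2/10) = 0.447 SD. Simulated error rates come from 400,000 trials. Favourable means significant in favour of the arm with stops; with no stops this is 2.5%, and total error is 5.0%.

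| ρ | Stops | Shift (SD) | Favourable | Total error |
|---|---|---|---|---|
| 0.3 | 1 | −0.051 | 3.2% | 5.2% |
| 0.3 | 2 | −0.095 | 3.9% | 5.5% |
| 0.5 | 1 | −0.085 | 3.9% | 5.5% |
| 0.5 | 2 | −0.159 | 5.2% | 6.4% |
| 1 (upper bound) | 1 | −0.171 | 6.2% | 7.5% |
| 1 (upper bound) | 2 | −0.318 | 11.0% | 11.6% |

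The sign depends on ρ. At ρ = 0 the shift is zero and the favourable rate stays at 2.5%. At ρ = −0.3, one stop gives +0.3 × 1.539/9 = +0.05 SD, against meditation, and a favourable rate of 2.0%.

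**Cross-check.** If stoppers' mean exceeds completers' mean by D, the completers-only bias is (k/n) × D in favour of meditation. For one stop in 10, D = 0.5, 1.0 and 1.5 SD give 0.05, 0.10 and 0.15 SD. For one stop among 20 pooled meditators the values halve to 0.025, 0.05 and 0.075 SD. For scale, the difference detectable with 80% power at 10 v 10 is about 1.25 SD (normal approximation).

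**Averaging over stops.** With number of stops Binomial(10, p), two or more counted as two, and ρ = 0.5:

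- p = 0.02: probabilities of 0, 1 and 2+ stops are 0.817, 0.167 and 0.016. Shift = 0.167 × (−0.085) + 0.016 × (−0.159) = −0.017 SD; favourable 2.8%, total error 5.1%.
- p = 0.05: probabilities are 0.599, 0.315 and 0.086. Shift = 0.315 × (−0.085) + 0.086 × (−0.159) = −0.04 SD; favourable 3.2%, total error 5.3%.

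At these assumed rates, the chance of at least one stop among 20 meditators is 1 − 0.98²⁰ = 33% or 1 − 0.95²⁰ = 64%.

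**The case against.** The strongest objection is to the direction. A reader might infer that the rules will tilt the result towards meditation. The documents do not support that. The MUSE rule concerns symptoms thought to come directly from using the device, and these may ease once use ends; a stopper might then score no worse at week 6 than a completer. The calculation also removes strictly the most distressed people, which the softer wording of the other two rules, and the physical triggers, do not imply. This stands: the bias is possible, not established.

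The second objection is size. The protocol states: "Meditation practice has very infrequent adverse effects". Severe mental illness is an exclusion. The averaged shift is a small fraction of the standard error. This also stands, although a single stop is not remote at the assumed rates.

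Third, controls are recruited after the first 20 participants complete, so meditation versus no treatment is not a randomised comparison in any case. The error rates above assume comparable groups and isolate this one mechanism. Later recruitment is a separate limitation and could matter more; it does not cancel this one.

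Fourth, attachments may provide for early exit. The point is therefore limited to the text available.

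A reader might also infer bias in NF-MM versus MM, since home practice is "6 weeks of NF-MM with MUSE or MM without MUSE at their homes" and the MUSE rule therefore bears on NF-MM alone during that period. But the other two rules cover both arms and largely overlap with it, and equal numbers of stops give no mean shift. Two stops against one at ρ = 0.5 would give about −0.07 SD, but nothing in the documents predicts such a split.

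**Conclusion.** The point holds in a limited form. The text ends study participation for symptom-related stops, describes no later affective scores for those people, and can have this effect before outcome measurement only in the meditation arms. An analysis of available scores could then favour meditation over no treatment, provided that someone stops and that stoppers would have scored worse at week 6 than completers. Neither condition is given in the documents, and neither is the use of available scores only; that is the natural reading of a regression with no missing-data rule.

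On the assumptions above, the bias is about 0.05 to 0.09 SD per stop in an arm of 10 for ρ of 0.3 to 0.5, and 0.02 to 0.04 SD averaged over stop rates of 2 to 5% at ρ = 0.5. It is nil with no stops or if symptoms resolve, and it reverses if stoppers do better. This is a minor weakness. It merits a change because the remedy is cheap and an uncollected week-6 score cannot be recovered.

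**What to change.** 1. In Complications of procedures, Psychological non medical risk, and Safety and outcomes monitoring, separate stopping the intervention from leaving the study.
2. In Study Site, invite anyone who stops early, in any arm, to complete the BAI, BDI-II and NSI by phone or online about 6 weeks after the pre-treatment visit. Make this optional, and apply the suicidal-ideation contingency plan to any BDI-II taken remotely.
3. In Biostatistical Analysis, state that affective comparisons keep everyone in the allocated group and use these scores. Report symptom-related stops and still-missing scores by arm.
4. For scores still missing, add a simple worse-outcome sensitivity analysis, for example setting each missing change 0.5, 1.0 and 1.5 SD worse than the completers' mean in that arm.

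The cost is a short amendment with consent wording, one contact and three questionnaires per stopper, and two counts per arm. People who felt worse would be asked to answer questionnaires, and some will decline, so the change reduces the problem without removing it. The estimate would describe being assigned to meditation, not continuing to practise it.

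### Participants who stop because of symptoms or distress leave the study with no outcome visit stated, so affective scores in the meditation arms can go missing because they are bad

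*Combined protocol and SAP*

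**What the plan says.** Three places in the combined protocol and SAP deal with participants who do badly on the intervention.

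- Risks and Discomforts, Complications of procedures. The trigger is "If these symptoms are believed to be stemming directly from use of MUSE and are intolerable for patients", and the consequence is "they will be instructed to discontinue participation in the study". The complaints listed just before it include anxiety, irritability, fatigue, headache and trouble falling asleep.
- Risks and Discomforts, Psychological non medical risk. Participants in whom meditation brings up unpleasant thoughts or feelings can contact staff and "if necessary will be discontinued from the study".
- Monitoring and QA, Safety and outcomes monitoring. The trigger is "If the practice of meditation or use of neurofeedback is causing significant psychological distress or physical discomfort", and then "the patient will be advised to discontinue participation".

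The outcome visit is set under Study Procedures, Study Site: "A post-treatment assessment session will take place within one week of completion of the intervention". No visit is stated for anyone who stops before completing. The Biostatistical Analysis section compares BAI, BDI-II and NSI across the three groups by linear regression. It names no analysis population and no handling of missing outcomes.

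**The concern.** Nothing visible in the document separates stopping the practice from leaving the study. A participant who exits for anxiety, irritability or distress therefore need not supply a post-treatment score, although those complaints are close to what the affective outcomes measure. The link is most direct for BAI and NSI, through the symptoms listed for MUSE. For BDI-II it runs through the two distress rules.

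The arms are not equally exposed. The no-treatment controls neither practise nor wear the device before their second test, so none of the three rules can remove them. At stake are the comparison of meditation with no treatment and of NF-MM with MM (Aim 2), and the within-arm changes (Aim 1). Acceptability of NF-MM (Aim 5) is also touched, because the qualitative interview is held at the same post-treatment session. The protocol says the results may inform whether the device is recommended to patients, so a loss that flatters an active arm matters.

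**Working it through.** **Which exits reach which arm before the post-test**

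| Exit rule | NF-MM | MM | No treatment |
|---|---|---|---|
| Intolerable symptoms attributed to MUSE | yes | no (device supplied only after the post-test) | no |
| Unpleasant thoughts or feelings from meditation | yes | yes | no |
| Significant distress or discomfort from meditation or neurofeedback | yes | yes | no |

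**Inputs.** The protocol gives 20 participants in NF-MM and MM together plus 10 controls, 20 + 10 = 30, which agrees with its stated total. It gives no SD, alpha, exit rate or split of the 20. Assumed here: 10 per arm, normal outcomes with higher scores worse, no true difference, a two-sided 5% t-test on completers only, and 1 or 2 exits.

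**Shift when the worst scores leave one arm only.** The expected largest two of 10 standard normal values are 1.539 and 1.001. The full-sample mean is 0, so the mean of those who remain moves by (sum of the removed values) / (number remaining):

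- lose the worst 1: 1.539 / 9 = 0.171 SD
- lose the worst 2: (1.539 + 1.001) / 8 = 2.540 / 8 = 0.318 SD

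**Exit only partly related to outcome.** If the tendency to exit correlates r with the outcome, the expected shift is r times these values. At r = 0.5:

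- lose 1: 0.5 × 0.171 = 0.086 SD
- lose 2: 0.5 × 0.318 = 0.159 SD

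**Both meditation arms lose people.**

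- NF-MM loses 2, MM loses 1: 0.318 − 0.171 = 0.147 SD, or 0.5 × 0.147 = 0.07 SD at r = 0.5
- equal numbers lost in the same way: about 0

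**False significance in favour of the arm losing more** (100,000 simulated trials, no true difference):

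| Loss | Exit removes the worst scores | r = 0.5 |
|---|---|---|
| none | 2.5% | 2.5% |
| 1 v 0 | about 6% | 3.9% |
| 2 v 0 | about 11% | 5.2% |
| 2 v 1 | 7.3% | 3.8% |

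The 1 v 0 and 2 v 0 rows fit meditation against no treatment best, because the controls have none of these exits. For NF-MM against MM, the 2 v 1 row and the equal-loss case are also plausible.

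**With everyone assessed and analysed as assigned**, the simulated bias is about 0 and the two-sided error rate is 4.9%.

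**The case against.** The strongest reply is that the loss may be small and need not favour NF-MM.

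- **Exit rates.** The protocol anticipates no significant adverse effects from MUSE, calls adverse effects of meditation very infrequent, and excludes severe depression, suicidality and disabling anxiety. One or two exits in 10 is an assumption. This stands, and the figures above are conditional on it.
- **Size.** With 10 per arm the trial has 80% power only for about (1.960 + 0.842) × √(2/10) = 1.25 SD, so a shift of 0.09 to 0.32 SD is modest beside what it could detect. This also stands.
- **Certainty of the loss.** One passage says only if necessary. Another advises rather than instructs, and does not name the study as what is left. The consent pages and the study schematic are not available and might provide for follow-up. This limits confidence, but nothing that can be read supplies the missing visit.
- **Direction.** Symptoms caused by the device may settle once it is stopped, so the missing score need not be the arm's worst. The results can therefore be biased; it cannot be said that they would be.

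Two stronger readings are tempting. A reader might infer that the loss falls chiefly on NF-MM. That arm does have one more exit, but the monitoring rule gives MM a comparable one at a threshold that reads no higher, and no rates by arm are given.

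A reader might also infer a safety gap, because participants are "asked to fill out the BDI-II form during pre- and post-test visits" and anyone who leaves misses the second form. The document does not show that this form is the only scheduled trigger for the suicidal-ideation plan. Weekly calls and a weekly safety review by a physician or psychologist are also scheduled, and the plan itself is in an attachment that cannot be seen.

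**Conclusion.** The point holds as a risk of informative missing data. The stated rules can remove affective outcomes from NF-MM and MM because those outcomes are bad, and cannot remove them from the controls. The resulting bias can favour meditation over no treatment. It can favour NF-MM over MM only if NF-MM loses more people.

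Under the assumptions above, one or two exits from one arm and none from the other are worth 0.17 or 0.32 SD if exit tracks the outcome fully, and 0.09 or 0.16 SD at a correlation of 0.5. A 2 v 1 loss between the meditation arms is worth about 0.15 SD or 0.07 SD respectively. Confidence is medium, because no exit rate is stated and some study documents cannot be seen. This is a cheap improvement rather than a fault that invalidates the design.

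**What to change.** Reword the three passages (Complications of procedures, Psychological non medical risk, Safety and outcomes monitoring) so that they agree with each other and distinguish stopping the practice from leaving follow-up. Who stops, and when, is left as it is.

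- Under Study Site, state that anyone who stops early and does not withdraw consent is still invited to the scheduled six-week post-treatment assessment: cognitive tests, BAI, BDI-II, NSI and CAMS-R.
- Under Biostatistical Analysis, state that these participants are analysed in their assigned arm.
- Record the reason for each stop and report numbers and reasons by arm, including those who decline the visit.

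The cost is changed protocol wording, with matching consent wording if needed, and a few assessments of people who stopped early. The documents contain no budget, so the cost of those assessments cannot be judged here. Some who stop will refuse, so the loss may shrink rather than vanish. Including people who stopped practising slightly dilutes the estimated effect of practice. Scores not collected at the time cannot be recovered later.
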